## **Additional measures**

In addition to the primary and secondary outcomes, we will collect index and presenting partners' socio-demographics, sexual orientation, sexual orientation disclosure status, HIV and other STDs testing history and HIV PS history.

## **Data management**

For the baseline and follow-up surveys for the indexes and the survey for partners, all data are directly entered into computers as participants complete the surveys. Data can be readily downloaded and converted to the format of commercially available statistical software. During collection of the online portion of the study, all data will be transmitted securely using SSL (TLS) 128 bit encryption across the Internet (HTTP). SSL provides users with the assurance of access to a valid, "non-spoofed" site, and prevents data interception or tampering with sensitive information. The SSL certificate that will be used for this project will use 128-bit encryption, the preferred security level of government and financial institutions. 128-bit encryption offers protection that is virtually unbreakable. Data will be located in a secured server at UNC Chapel Hill. The server will be configured with redundant hard drive array to ensure reliability. Access to the data will be password protected within the server's firewall. Only the PI and a designated senior staff member will have the password to access to the "key" that links the non-descript identifier to personally identifiable information. IP addresses of participant's computers will not be collected at any time. Cookies will not be used in any way to track participant activity. A

quick link will exist on each survey page to provide participants a rapid way to switch to an innocuous website if their privacy is interrupted while completing the survey.

No presentation or publication of the study results will refer to participants individually. Manuscripts published regarding this work will be based on the accumulated database. Exceptions to confidentiality for participants are those required by law and include suspicion of child abuse, elder abuse, and threat of imminent action on suicidal or homicidal ideation. Participants will be informed of these exceptions in the informed consent process.

## Statistical Analysis Plan

For the primary outcomes of feasibility and acceptability of the intervention: this will be analyzed through descriptive analysis to assess the feedback on the feasibility and acceptability of the crowdsourced PS intervention among index MSM and their partners in the intervention group. For the primary outcome of the proportion of partners returning for HIV testing within 3 months of the index participant's enrolment in the study, log-binomial regression (generalized linear model with binomial distribution and log link) will be used to calculate 95% confidence intervals for the proportion of notifiable partners visiting by arm. Risk differences and risk ratios will also be calculated in these models. As this study is a pilot RCT, and we will only recruit 120 index MSM, and they will be randomly assigned in a 2:1 ratio, adjustment for covariates would be necessary if the two study arms are not balanced. In secondary analyses, we will adjust for pre-specified potential confounding variables that might bias the estimate if not accounted for (e.g. index age, index marital status). If a partner reports more than one index referred him, he will be counted as a returning partner for each identified index.

*Table 1* Analysis strategies for secondary outcomes

Secondary Outcome	Population	Model Type
The proportion of reported partners being notified by indexes among all reported partners	Reported sexual partners	Binomial regression, robust variance
Mean number of partners tested per index participant	Index participants	Poisson or negative binomial regression, robust variance
The proportion of positive HIV tests among tested partners	Tested sexual partners	Binomial regression, robust variance
Mean number of partners with HIV (case-finding) per index participant	Index participants	Poisson or negative binomial regression, robust variance
The proportion of reported partners getting HIV testing who are not spouses or regular partners	Reported casual male sexual partners	Binomial regression, robust variance
The proportion of presenting partners reporting condom use during the last anal intercourse	Presenting sexual partners	Binomial regression, robust variance

Subgroup analyses will be performed by partner type (e.g. main male partner vs. casual male partner). For secondary outcomes, analysis approaches are provided in Table 1. For count variables expressed as the mean number of partners, we will use either Poisson regression or negative binomial regression if overdispersion is identified. In addition, we will assess which secondary outcomes seem to have meaningful discriminatory power in a future study. We will include the potential secondary outcomes that are important and meaningful discriminatory

power in the future study. In addition, we will use the information we obtain in the pilot RCT to conduct sample size estimation for the later trial.

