However, barriers from both health providers and index patients limit its efficacy. As a result, PS is underused in many countries, including China where only 15.7% of index HIV case spouses were notified. In addition, tailored PS for MSM who usually have multiple male or female partners are limited, especially in China. Conventional PS in China use passive referral by providing index patients with partner referral cards, and PS via disease intervention specialists is not available in China. One study conducted among Chinese MSM revealed that only 267/1225 (21.8%) partners of the index cases were successfully notified and tested. Our preliminary data showed that only 16.2% (18/111) of HIV infected MSM have notified their casual partners in 2016. The low frequency of routine PS programs suggests that current strategies reach only a fraction of those at risk. Many existing HIV PS programs lack a patient-centered focus and are ill-suited to addressing issues faced by many MSM. Few incorporate high-risk individual preferences are tailored to the needs and concerns of MSM, or incorporate preferences and suggestions from the local community. Thus, identifying an innovative method to improve the efficacy of PS is critical for HIV control in China and other middle-income countries. Successful PS programs for MSM in China and other LMICs will require novel methods to reach an MSM population where condomless sex and casual sexual partnerships are common, and where severe stigmatization restricts healthcare access among MSM.

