## Methods and study design

### Study design overview

This study will use a pilot RCT comparing the crowdsourced PS intervention to standard PS. In China, a passive referral is the only existing PS model for HIV PS. We will conduct a pilot study to refine the components and procedures of the intervention and test the feasibility and acceptability of the crowdsourced PS intervention. Newly identified MSM HIV cases will be recruited from Guangzhou. After completion of a baseline survey, eligible MSM will be randomized individually to either the crowdsourced intervention or conventional PS (control arm) in a 2:1 ratio. In both arms, partners will be instructed to report to the study site sites for HIV testing and will complete a brief sexual history questionnaire upon presentation. We will re-contact them within three months of enrolment to confirm whether the intervention or control PS procedures were implemented by the index. The primary outcome will be 1) the feasibility and acceptability of the intervention; 2) the preliminary impact of the intervention: by comparing the proportion of partners getting HIV testing between the intervention and control groups. Secondary outcomes will be the number of partners getting notified, the number of testing partners with confirmed HIV, and risk behaviors of partners. We will also observe these secondary outcomes among main male partners and casual partners separately. We hypothesize that: 1) a crowdsourced PS approach is feasible and acceptable, 2) as compared to conventional PS, will yield: a) more sexual partners reporting for HIV testing; b) more sexual partners getting notified; c) more sexual partners with confirmed HIV; and d) a set of sexual partners with greater STI risk behaviors, such as more receptive anal intercourse, and less condom use.

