## **Randomization**

Eligible participants will be randomly assigned to the crowdsourced PS arm (intervention arm) or conventional PS (control arm) in a 2:1 ratio. Since information under the control situation is already available from Guangzhou, a 2:1 ratio will allow us to spend more resources on intervention, and collect more primary outcome relevant data from participants in the intervention group (especially for the measure of the feasibility and acceptability). This approach ensures that the index participants in each arm will be evenly distributed. The number of partners

may vary somewhat across the two arms, as the number of partners of the index participants is variable. However, the total number of partners in the two arms should be comparable.

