### Intervention

Crowdsourced PS procedures: After randomization, the procedures for the crowdsourced intervention arm will be explained to the MSM HIV index cases in this arm. Final procedures will be determined upon completion of crowdsourcing events. The expected procedures are shown below:

1. MSM in the intervention arm will *receive the crowdsourced intervention* at the study site.
2. Index MSM will *choose specific crowdsourced materials* to use for notification of each partner.
3. The index cases will then *choose the procedure* to be used for delivery of the intervention: a) personally send to partner, b) have the study coordinator send, c) have the CBO send, d) send through an anonymous email/phone number system, or e) any combinations of the above-mentioned procedures.  
The crowdsourced intervention package may be delivered by text, WeChat, gay dating apps, and/or email. If the index is not ready to send the message to the partner at the time of the clinic visit, he may contact the research coordinator at any time within 6 weeks to request that the materials be sent.
4. The index patients will *select a message* about the crowdsourced intervention. The texts/emails will include a unique ID, address of the center, and phone number/WeChat ID of the study coordinator at the center. The specific content will be refined in the crowdsourcing events.
5. *The message will be sent to the partners* through a prechosen delivery channel, coupled with prechosen crowdsourced intervention materials.
6. *Partners* who view the intervention materials *will be prompted* to enter a phone number, email address, WeChat ID, and usernames for Blued (A popular gay dating mobile application with 43 million users in China). These data allow us to link partners who view the intervention materials to the index cases.
7. At the conclusion of the intervention materials, *information will be provided* about the MSM community centers where HIV testing is available, research coordinator's contact information, and instructions to retain the email/text to present at the center. If the partner is willing to provide a phone number or email address, *a message will be automatically generated* including the center and coordinator information.
8. *Partners will be encouraged* to present for testing within one week of notification.

9. *Index MSM will also be given PS cards*, comparable to the standard PS arm, in case they choose to inform partners this way

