In addition, after introducing the crowdsourced intervention to the participants in this group, a short survey that aims to evaluate the feasibility and acceptability of the crowdsourced intervention will be carried out.

Conventional PS procedures: The index cases in the conventional PS arm will be provided with referral cards that include the unique ID to link index and partners, as well as the address of the study centers where they can present for free HIV testing and the phone number of the study coordinator. The index cases will be encouraged to remind their partners to bring the referral card with them when they present. On the reverse side of the card, we will provide instructions to facilitate forwarding of test results if the partner chooses to attend a different clinic. Guangzhou CDC will also coordinate with other clinics in the city to collect the cards and a brief consent to capture the HIV result.

Partner linkage: Partners will be linked to the indexes through the unique ID on the referral cards. Partners without unique ID information will be matched to the index using a sequential matching algorithm using all index identification information provided. If a partner is unable to produce the card/text/email, we will ask him/her how he/she was originally notified of the need for testing. If the partner indicates he/she was informed by intervention materials, we will ask him/her to identify the phone number, email address, or username to which the message was delivered. We will also ask him/her to provide the date that he reviewed the intervention materials. If a partner was given a referral card but cannot present the card, we will ask him/her to give the name or contact information of the person who gave him/her the card. We will also obtain the date that the card was provided. Partners without card/text/email will be matched to the index using a sequential matching algorithm using all index identification information provided.

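### The primary partner-level model makes no allowance for partners who share an index, so its 95% intervals come out too narrow

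*Combined protocol and SAP*

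**What the plan says.** The protocol's Study design overview makes the index man the unit of randomisation: "eligible MSM will be randomized individually to either the crowdsourced intervention or conventional PS (control arm) in a 2:1 ratio". Under Primary outcomes, the impact measure is the proportion of partners tested within three months of the index's enrolment, so the unit of analysis is the partner.

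For that measure the Statistical Analysis Plan states that "log-binomial regression (generalized linear model with binomial distribution and log link) will be used to calculate 95% confidence intervals" for each arm's proportion, and takes the risk ratio (RR) and risk difference (RD) from the same models. It gives a distribution and a link but no variance method.

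Table 1 covers secondary outcomes only. All six rows specify robust variance. Four are partner-level proportions, listed as "Binomial regression, robust variance" with no cluster named; the other two are counts per index.

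Three further statements bear on the point:
- Background describes "MSM who usually have multiple male or female partners".
- Randomization says that "the number of partners of the index participants is variable".
- The Statistical Analysis Plan adds: "If a partner reports more than one index referred him, he will be counted as a returning partner for each identified index".

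**The concern.** A binomial GLM with its default variance counts every partner record as a separate piece of information. Here the records come in groups, one group per randomised man, and members of a group share a cause. In the intervention arm the index picks the materials, the channel and the timing; the Intervention section provides for delay: "If the index is not ready to send the message to the partner at the time of the clinic visit". In the control arm he decides whether to hand over the referral cards. His readiness to disclose therefore acts on all his partners' chances of being tested, which points to positive correlation within index.

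If so, the intervals for the arm proportions, the RR and the RD claim more information than 120 randomised men provide. The plan says that the pilot is not powered to compare the arms and specifies no test, so the estimate and its interval are the whole comparative result for this primary outcome. The plan also intends to use the pilot's information to size the full trial. The descriptive feasibility and acceptability analyses are not affected.

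**Working it through.** **The plan's own figure.** Sample size and power gives a minimal detectable effect of 26.7% with 80 and 40 indexes, a 30% control return rate, alpha 0.05 and power 0.80. The pooled two-sided formula for two proportions gives 26.6 points at a 30% control rate and 26.7 at 31%; power for 30% against 56.7% is 80.2%. The figure reproduces by treating 80 and 40 as independent binary observations. It contains no clustering term, so it does not supply the allowance missing from the model.

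**Inputs.** From the documents: 80 and 40 indexes, 30% return. Assumed, because the documents are silent: mean partners per index 2 to 4, ICC 0.1 to 0.3, and three shapes for the number of partners *m*: equal; mildly variable (1 + Poisson); skewed (1 + geometric).

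**Standard error.** Correct SE ÷ as-written SE = √(1 + (E[m²]/E[m] − 1) × ICC). For mean 3 and ICC 0.2:
- Equal: E[m²]/E[m] = 3, so √(1 + 2 × 0.2) = 1.18.
- 1 + Poisson: E[m²] = 9 + 2 = 11, 11/3 = 3.67, so √(1 + 2.67 × 0.2) = 1.24.
- 1 + geometric: E[m²] = 9 + 6 = 15, 15/3 = 5, so √(1 + 4 × 0.2) = 1.34.

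**RD interval in that example.** There are 80 × 3 = 240 and 40 × 3 = 120 partners. As written, the half-width is 1.96 × √(0.21/240 + 0.21/120) = 10.0 points. Multiplied by the three ratios, it should be 11.9, 12.4 or 13.5 points.

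**Coverage.** Beta-binomial simulation, 20,000 replicates per setting, 30% return in both arms. The as-written variance of the log proportion in each arm is (1 − p)/(Np), where N is the number of partners. The clustered version is Σ(y − mp)²/(N²p²), summed over indexes, times n/(n − 1) for n indexes, with t on 118 df.

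| Setting | SE ratio: equal / Poisson / skewed | Coverage of nominal 95% RR interval, as written |
|---|---|---|
| Mean 2, ICC 0.1 | 1.05 / 1.07 / 1.10 | 94.0% / 93.8% / 93.5% |
| Mean 3, ICC 0.2 | 1.18 / 1.24 / 1.34 | 90.8% / 89.1% / 86.2% |
| Mean 4, ICC 0.3 | 1.38 / 1.46 / 1.67 | 84.6% / 82.4% / 76.6% |

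Clustered RR intervals covered 94.0% to 95.5% across these assumptions. With ICC 0 (1 + Poisson, mean 3) the as-written interval covered 95.1%, so the loss comes from clustering. At mean 1.5 and ICC 0.05 the SE ratio is 1.02 and coverage 95.1%.

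**Why Table 1 needs the cluster named.** In a model with arm only, a sandwich variance computed on partner rows is Σ(y − p)²/N² for each arm. For a yes/no outcome this equals p(1 − p)/N, the ordinary binomial variance. Robust variance without a cluster therefore changes nothing. The two per-index count rows already have the right unit.

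**The case against.** **The plan is silent on variance; it does not commit to independence.** Table 1 gives robust variance for every partner-level proportion, so a phrase may simply have been dropped from the primary sentence. That is plausible. But the table is limited to secondary outcomes, and an analyst following the text would fit the default. Carrying the phrase over would still leave the cluster unnamed.

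**The direction needs a positive ICC, and none is given.** Materials are chosen partner by partner, and a man who tells his main partner but not his casual partners would lower the correlation. This stands as a limit on how precisely the size can be stated, and it is why a range is shown. It does not make independence a sound default when one man governs notification of all his partners.

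**Shared partners can act either way.** If the indexes who share a partner are in the same arm, the double count makes intervals too narrow. If they are in different arms, the same outcome enters both sides, and an independence-based interval for the RR or RD becomes too wide. That is correct. Sharing adds dependence but is not in itself evidence for narrow intervals, and it was not simulated. A variance cluster that joins such indexes handles both cases, though it reduces the number of clusters and may span arms.

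**The consequence is limited in a pilot.** Clustering the variance leaves the proportions, RR and RD unchanged, and the plan does not say that the intervals themselves will size the next trial. Both points are fair, and they confine the harm to overstated precision. They do not make an invalid interval acceptable as the reported result.

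**Clustered intervals are not perfect.** Clustered RD coverage was 93.8% in the skewed corner (mean 4, ICC 0.3), slightly below nominal. That is still far better than the as-written interval.

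**Conclusion.** The concern holds. The primary analysis is at partner level, randomisation is at index level, and no part of the plan links the two in the variance. As written, the 95% intervals for the arm proportions, RR and RD are too narrow whenever partners of one index are positively correlated and some indexes have more than one partner. The documents expect the second and describe a mechanism for the first.

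The size rests on the assumed partner counts and ICC. The lower figure, an SE understated by about 5%, is a minor loss; the 76.6% coverage is the extreme corner of the assumed range. A middle case (mean 3, ICC 0.2) gives coverage of 86% to 91%. This should be corrected before analysis: a primary interval is wrong as specified, and naming the variance in advance avoids choosing it after the results are seen.

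**What to change.** In the Statistical Analysis Plan:

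1. Fit the primary log-link model as a GLM, or by GEE with independence working correlation so that the estimand stays the proportion of partners, with sandwich variance clustered on the index participant.
2. Add a small-sample correction, given 40 control clusters, and name modified Poisson as the fallback if the log-binomial model does not converge.
3. Obtain the RD by standardisation or an identity link, with the same clustered variance.
4. Put indexes who share a partner in one variance cluster, with each record keeping its own index's arm.
5. In the four partner-level rows of Table 1, write *robust variance clustered on index participant*, and use the same variance for the partner-type subgroups.
6. Preferably, report the ICC by arm for sizing the full trial.

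Item 1 and the clustered variance in items 3 and 5 are the core repair; the rest makes it complete. The cost is wording only. The protocol already provides that "Partners will be linked to the indexes through the unique ID on the referral cards", with a matching procedure for partners who present without an ID, so the cluster identifier exists and no new data, visits or participants are needed. The intervals will be wider.

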## **Baseline questionnaire**

After enrolment, participants will complete a brief self-administered baseline questionnaire. Study staff will be available to assist in the event of confusion about specific questions or if participants do not have a sufficient reading level to complete the survey on a tablet. The questionnaire will address socio-demographic characteristics and HIV testing history. A more detailed, partner-centric sexual history will be obtained by focusing on sexual partners in the previous six months. The sexual history will include specific behaviors with individual partners, including receptive/insertive anal sex, performing/receiving oral sex, condom use, and frequency of each type of intercourse. Information on sexual orientation and sexual orientation disclosure status will also be collected. Detailed contact information will be obtained for the participants and sexual partners for the past six months. Contact information will include phone number, email address, WeChat ID, QQ ID, and smartphone-based sex-seeking applications ID (i.e., Blued ID).

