### Sample size and power

This is a pilot RCT, and the primary outcomes of this study are: 1) to test the feasibility and acceptability of the crowdsourced intervention, and 2) to pilot the preliminary impact of crowdsourced PS intervention in promoting HIV testing among partners of the newly identified HIV cases. In addition, this pilot RCT aimed to collect preliminary data for the designing of a full RCT, which aimed to measure the efficacy of the crowdsourced PS intervention in promoting PS. Thus, the sample size of this study is not designed and will be not powered enough to test the difference between the two arms. However, with a sample size of 120 (80 for intervention arm and 40 for the control arm, respectively), this pilot study would collect enough information to measure the feasibility and acceptability of the intervention, and it will be able to observe the differences between the two arms and collect preliminary data for an adequate sample size calculation of a full RCT. With a sample size of 120 (ratio of 2:1), alpha=0.05, power=0.80, and the partner return rate in the conventional PS arm is 30% (around 31% in 2016 in Guangzhou), the minimal detectable effect size would be 26.7% for this pilot study.

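### Does the undefined term for the primary testing denominator leave the primary comparison without an analysis population?

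*Combined protocol and SAP*

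**What the plan says.** The design overview describes the preliminary-impact outcome as assessed "by comparing the proportion of partners getting HIV testing between the intervention and control groups". The Primary outcomes section fixes the numerator (attendance at a centre, or verification in the CDC database) and the time window (three months from the index's enrolment). Neither section qualifies the word partners. The Statistical Analysis Plan then fits a log-binomial model for "the proportion of notifiable partners visiting by arm". Table 1 has a population column, but it covers the secondary outcomes only.

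Other sections bear on who the partners are:

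- **Timing of the list.** "After completion of a baseline survey, eligible MSM will be randomized individually" (Study design overview), and at that survey "Detailed contact information will be obtained for the participants and sexual partners for the past six months" (Baseline questionnaire).
- **Partner number.** The Randomization section treats it as a characteristic of the index: "the number of partners of the index participants is variable".
- **Linkage.** "Partners will be linked to the indexes through the unique ID on the referral cards" (Intervention). A partner informed by the intervention materials who cannot show the card, text or email is asked for the contact route: "we will ask him/her to identify the phone number, email address, or username to which the message was delivered".
- **Counting.** Under the Statistical Analysis Plan, a partner referred by several indexes counts once for each index identified.

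**The concern.** A primary proportion needs a denominator, and the analysis text uses a word that appears nowhere else. *Notifiable* could mean every partner listed at baseline or only those for whom contact details were recorded. At a stretch it could mean those actually notified. The follow-up survey also asks about new partners, and a referral card identifies the index rather than a named partner. So late-named partners, or people who attend without being on the list, might enter the count.

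At stake are the arm proportions and the risk difference, and in some cases the risk ratio. The plan intends to use pilot information to size a later trial, so a proportion on an unknown base could mislead that calculation. A denominator chosen after seeing the data would also be an avoidable freedom on a stated primary outcome.

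**Working it through.** **1. The plan's own figure.** The sample-size section assumes that "the partner return rate in the conventional PS arm is 30" per cent, with 40 control and 80 intervention participants, alpha 0.05 and power 0.80, and states a detectable effect of 26.7%. Check it with the pooled two-sided normal approximation at 30% against 56.7%:

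- Pooled proportion: (40 × 0.300 + 80 × 0.567)/120 = 0.478
- Null SE: √[0.478 × 0.522 × (1/40 + 1/80)] = 0.0967
- Alternative SE: √[0.30 × 0.70/40 + 0.567 × 0.433/80] = 0.0912
- z = (0.267 − 1.96 × 0.0967)/0.0912 = 0.85, so power is 0.802

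The figure reproduces, but its units are index participants. It does not identify a partner denominator.

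**2. What the text implies.**

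- The only partner list made before allocation is the baseline one. Its six-month window matches the third eligibility criterion.
- Secondary outcome 5 and its Table 1 row are the primary endpoint, testing, restricted to casual partners. The population there is reported partners.
- Secondary outcome 1 and its Table 1 row treat notification as an outcome among reported partners. Notified partners are therefore a numerator elsewhere in the plan, not its base population.
- The follow-up survey asks about notification and testing of the specific partners, the expression it has just used for those named previously. Nothing places new partners in the primary denominator.

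These point to all partners reported at baseline.

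**3. How much the other readings could move the result.** The documents give no partner counts or contact shares. Assume three listed partners per index (120 control, 240 intervention), with 36 and 96 tested.

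| Reading | Control | Intervention | RD (points) | RR |
|---|---|---|---|---|
| All listed | 36/120 = 30.0% | 96/240 = 40.0% | 10.0 | 1.33 |
| 90% have details, all tested among them | 36/108 = 33.3% | 96/216 = 44.4% | 11.1 | 1.33 |
| 70%, same condition | 36/84 = 42.9% | 96/168 = 57.1% | 14.3 | 1.33 |
| 50%, same condition | 36/60 = 60.0% | 96/120 = 80.0% | 20.0 | 1.33 |
| 70%, testing unrelated to details | 25.2/84 = 30.0% | 67.2/168 = 40.0% | 10.0 | 1.33 |
| 70%, six tested per arm lack details | 30/84 = 35.7% | 90/168 = 53.6% | 17.9 | 1.50 |

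Equal contact shares alone do not preserve the risk ratio. The fraction of tested partners with details must also be equal in the two arms, as the last row shows.

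For scale, the all-listed risk difference has SE √(0.30 × 0.70/120 + 0.40 × 0.60/240) = 0.0524. That is 10.0 ± 10.3 points before any allowance for clustering within index. Even the 20.0-point result lies inside that interval.

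**4. Late-named partners and unlisted attenders.** Take a true null (36/120 and 72/240) and add untested late-named partners. Adding 12 and 48 gives 36/132 against 72/288, RR 0.92. Adding 24 and 24 gives 36/144 against 72/264, RR 1.09. For unlisted attenders, start from RR 1.33. Adding 2 and 14 gives 38/122 against 110/254, RR 1.39; adding 7 and 4 gives 43/127 against 100/244, RR 1.21. The direction depends wholly on the numbers assumed.

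**The case for a change.** The strongest case for a change is that the analysis text chose a word other than *reported*, which stands in Table 1 of the same section. Since contact details are collected separately, *notifiable* could well mean reachable. On that reading the later trial could be sized differently. By the two-proportion formula (two-sided 0.05, power 0.80, no clustering), 30.0% against 40.0% needs 356 listed partners per arm. 42.9% against 57.1% needs 192 with details, or 192/0.7 = 274 listed. A definition would cost only a few words.

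Part of this stands. The term is undefined, and no sentence says outright how to treat someone who attends, links to an index and matches no listed partner. The multiple-referral rule does not settle that case, because it was written for another purpose. It does, however, count by identified index, and the linkage procedure also matches to the index, so the plan leans towards counting such a person for that index.

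The rest does not call for a change. The 70% share, and the condition that every tested partner falls within it, are assumptions. Hand-delivered cards in the control arm need no recorded details, so the condition is doubtful there. Both baseline denominators come from the same questionnaire, so whoever designs the later trial can compute either.

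**Conclusion.** The concern does not require a change. The plan omits a definition, and its other sections supply a sensible one: all past-six-month partners reported at the baseline questionnaire, with returners counted by identified index. That denominator is fixed before allocation and so carries no post-randomisation selection.

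Under the assumed counts, the contact-details reading moves the risk difference from 10.0 to between 11.1 and 20.0 points at shares of 90% to 50%. It does not move it at all if testing is unrelated to recorded details. The risk ratio changes only if the contact shares or the share of tested partners with details differ between arms. None of these quantities is in the documents, so no actual distortion has been shown.

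The consequences are limited. The sample-size section says the study is not powered to compare the arms, and feasibility and acceptability are assessed descriptively. The Table 1 analysis of partners tested per index does not depend on the partner denominator. The conclusion would differ if the primary proportion were restricted to partners actually notified, or if late-named partners were added to its base; the text supports neither.
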